- Posthepatic resection (the second phase), begins once the specimen has been delivered and hemostasis secured. During this phase, an attempt is made to return the patient to normovolemia. For our standard fluid management, blood loss is replaced volume to volume with albumin and crystalloid (6 cc/kg/hr x total operative time) will be infused to achieve the assumed fluid requirement (third space). After this fluid therapy, if BP<90mmHg or urine output< 25ml/hr, additional fluid boluses either colloid or crystalloid are given. Packed red-blood cells (PRBC) are included in resuscitation if the hemoglobin <7 g/dL. Fresh-frozen plasma (FFP) or platelets may be given at the request of the surgeon if surgical hemostasis is inadequate, international normalized ration (INR) >1.8 or platelets < 80,000 mL.

The GDT arm will have fluid therapy guided by the Edwards EV1000 system. First, blood loss will be replaced 1:1 volume with albumin. After this infusion, additional fluid will be given based on the patient's SVV. If this value is greater than 2 standard deviations of the baseline value more albumin will be given until SVV is less than or equal to no greater than 2 standard deviations above the baseline SVV. If the SVV is at baseline or not greater than 2 standard deviations from the baseline value, no additional bolus fluid will be given (Appendix 1). The maintenance crystalloid fluid will continue at 1cc/kg/hr that was begun in the LCVP phase. Group and protocol assignment will be maintained from the beginning of the reconstruction phase during the index operation, until after the patients are transferred to the PACU and receive standardized postoperative management at the discretion of the treating physicians.

During the intervention period, continuous non-invasive pulse wave analysis will be performed (Edwards EV1000) and the information stored in the monitor. Download is enabled to a USB port and memory stick. In the group assigned to standard management the monitor will be covered and the data derived from it will not be available to the anesthesia care team; this blinding will only be removed for the involved researchers at the completion of the study for retrospective analysis and comparison. At this time only research staff and anesthesia staff will have knowledge of patients randomization assignment.

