10.0 EVALUATION DURING TREATMENT/INTERVENTION

- Preoperative data will be collected and recorded: date of birth, weight, height, complete metabolic panel, complete blood count, coagulation profile.
- Standard intraoperative monitoring will be carried out for all patients.
- GDT patients will also be monitored by CO, SV and SVV. These data will similarly be obtained and recorded for the patients in the standard management group but it will not be available for the treating practitioners.
- Further measures of end-tissue perfusion will be assessed with arterial lactate levels and DO₂ (oxygen delivery) at baseline (before incision), at completion of the resection phase (intraoperatively), upon arrival to PACU (0 hours postoperatively), and on the morning of POD #1.
- Assessment and recording of all intraoperative and postoperative complications; the latter being considered as those occurring on or after postoperative day 1 until postoperative day 30. Complications occurring intraoperatively and after surgery on

MEMORIAL SLOAN-KETTERING CANCER CENTER
IRB PROTOCOL

IRB#: 12-056 A(4)

the same day, are most likely technical in nature and will be considered perioperative complications in the analysis.

- Estimated operative blood loss.
- Cumulative volume used for resuscitation will be recorded (stratified by colloids and crystalloids)
- Total dose (mcg/kg) of pressors, inotropes or vasodilators used will be recorded and stratified by specific drugs.
- Volume and type of blood products transfused.
- Daily comprehensive metabolic panel, complete blood count (these will be recorded for seven days or until discharged if discharged earlier).
- Daily coagulation panel, discontinued by POD 3 if normal.
- Volume and type of fluid intake and output until POD 7 or patient tolerates oral intake of fluids > 400 ml/24 hrs
- Daily nasogastric tube drainage volume (if used) and length of NG drainage
- Daily weight until POD 7 or until patient tolerates oral intake of fluids > 400 ml/24 hrs.
- Day of tolerating oral intake of fluids > 400ml/24hrs
- Day of IV ≤ KVO
- Day of tolerating oral intake of solids
- Day of passage of flatus
- Day of foley removal.
- Day of passage of feces
- Day of discharge

Table 2. Details hemodynamic and laboratory values obtained at different stages. For laboratory values a 30 minute variation will be allowed to account for early or delayed sample collection in the PACU and/or surgical ward.

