12.0 CRITERIA FOR THERAPEUTIC RESPONSE/OUTCOME ASSESSMENT

The null hypothesis is that GDT in patients undergoing liver resection does not alter the incidence of postoperative complications. A 15% decrease (from 30% to 15%) in the

MEMORIAL SLOAN-KETTERING CANCER CENTER IRB PROTOCOL

IRB#: 12-056 A(4)

incidence of 30-day complications will be considered clinically significant and will represent the primary outcome measure. The incidence of these will be assessed after each patient's postoperative visits.

Secondary outcomes include the impact of GDT on low cardiac output time, total volume of fluid used perioperatively, the requirement for blood transfusion, the total dose of vasoactive drugs, end-organ perfusion markers and the net fluid balance 48 hrs postoperatively.

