14.0 BIOSTATISTICS

This is a randomized comparison of goal-directed compared to standard fluid management in patients undergoing liver resection. Primary endpoint is overall postoperative morbidity.

270 patients will be randomized 1:1 to the two arms. This sample size provides 80% power for detecting a 15% decrease in the proportion of overall postoperative complications (i.e regardless of grade of severity), assuming the standard arm will have a 30% complication rate (two-sided Type I error of 5%). It also allows for an interim analysis halfway through enrollment, using O'Brien-Fleming boundaries both for efficacy and futility. If $p \leq 0.005$ at the interim analysis enrollment will stop with the conclusion that goal-directed fluid management significantly decreases postoperative morbidity. If $p \geq 0.468$ at the interim analysis enrollment will stop with the conclusion that goal-directed fluid management does not significantly decrease postoperative morbidity. If $0.005 < p < 0.468$ then the trial will continue to full enrollment. With an approximate enrollment of 11 patients per month, accrual should be complete in 2 years.

Secondary endpoints will be compared between the two arms using the Wilcoxon rank-sum test, except for the categorical endpoints of blood transfusion and systemic inflammatory response, which will be compared using Fisher's exact test.

MEMORIAL SLOAN-KETTERING CANCER CENTER IRB PROTOCOL

IRB#: 12-056 A(4)

Since one of our main goals for this study is to establish what the individual amount of resuscitation is for each patient, tailored to their hemodynamic status, we decided to use their baseline value ± 2 standard variations as their homostatic stroke volume variation. An elevation above 2 standard deviations would be statistically unlikely to represent a normal variation of the measurement and will thus be considered a hemodincomically significant deviation from baseline.

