15.2 Randomization

This is a single-blinded randomized trial. After eligibility is established and consent is obtained, patients will be registered in the Protocol Participant Registration (PPR) system.

Eligible patients will be consented for the trial prior to surgery. However randomization will not occur until the operating room. After the liver has been resected, intraoperative randomization will be done by envelopes. Randomization will be stratified by diagnosis (metastatic liver disease compared to primary disease where primary disease will encompass liver cancer and extrahepatic biliary cancer).

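### The primary analysis names no test or covariate and leaves out the diagnosis stratum, although post-resection randomisation makes extent of resection and prior blood loss valid baseline covariates; the cost is modest precision, not validity

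*Combined protocol and SAP*

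**What the plan says.** - **Timing and stratification.** Sections 4.1 and 15.2 place envelope randomisation in the operating room after resection. Section 15.2 adds: "Randomization will be stratified by diagnosis", meaning metastatic against primary disease. No other factor is named.
- **Blood loss.** Section 4.1 opens the post-resection phase by replacing blood loss in both arms. In the standard arm "blood loss is replaced volume to volume with albumin", and the goal-directed arm also starts with a 1:1 albumin replacement. Section 10 lists "Estimated operative blood loss" for recording, which is a total for the operation.
- **Extent of resection.** It does not appear in the section 10 list, in the text available to this review.
- **Primary analysis.** Section 14 states: "Primary endpoint is overall postoperative morbidity". It gives a sample size, a target difference and interim p-value cut-offs of 0.005 and 0.468, but no test, model or covariate for the primary comparison. The methods it does name (Wilcoxon rank-sum and Fisher's exact) are for secondary endpoints.

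**The concern.** In most surgical trials the extent of resection and the bleeding during transection come after randomisation and cannot safely be adjusted for. Here they come before it. Treatment cannot affect them, and both plausibly predict complications. Section 14 makes no provision for them, nor for the one factor the trial does stratify on.

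Two things are at stake. The first is precision: a prognostic baseline covariate narrows the interval around the treatment effect without more patients. The second is credibility. With 135 per arm, some imbalance in extent or blood loss is likely by chance, and readers will ask about it because blood loss also sets the first replacement volume. An adjustment chosen after the data are seen would carry little weight; one written down beforehand would.

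**Working it through.** **Inputs from the documents.** Section 14: "This sample size provides 80% power for detecting a 15% decrease in the proportion of overall postoperative complications", "assuming the standard arm will have a 30% complication rate", and a "two-sided Type I error of 5" per cent. Section 12: "A 15% decrease (from 30% to 15%) in the" incidence of 30-day complications. N = 270, or 135 per arm.

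**Inputs assumed.** The prognostic strength of extent and blood loss is not given anywhere, so ranges are used.

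**1. Reproduce the plan's figure.** With p1 = 0.30, p2 = 0.15, mean 0.225 and d = 0.15:

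- n = [1.96·√(2·0.225·0.775) + 0.8416·√(0.30·0.70 + 0.15·0.85)]² / d² = (1.1575 + 0.4889)² / 0.0225 = 120.5, so 121 per arm (242 in total).
- With continuity correction: n′ = (n/4)·[1 + √(1 + 4/(n·d))]² = (120.5/4)·(2.105)² = 133.5, so 134 per arm (268 in total). This matches 270.

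**2. Unadjusted power at 135 per arm, fixed design.**

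- Uncorrected: Φ[(0.15·√135 − 1.1575)/0.5809] = Φ(1.008) = 84.3%.
- Continuity-corrected, with d reduced by 1/135: Φ(0.859) = 80.5%.
- With the stated interim cut-offs applied to the uncorrected test (2,000,000 simulated trials, final level assumed 0.05 or 0.048): about 82%. The continuity-corrected test was not simulated under the interim rules.

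**3. Gain from adjustment, by simulation.** 4,000 trials per row, fixed design, marginal rates held at 30% and 15%. The covariates were a 50% binary factor (extent) and a standardised continuous one (blood loss).

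| Assumed OR, extent / blood loss per SD | Unadjusted | Adjusted | Change (points) |
|---|---|---|---|
| 1 / 1 (uninformative) | 85.5% | 84.8% | −0.7 |
| 1.5 / 1.3 | 84.7% | 85.0% | +0.3 |
| 2 / 1.5 | 85.0% | 86.1% | +1.1 |
| 3 / 1.8 | 85.2% | 87.8% | +2.6 |

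The Monte Carlo standard error of each power is √(0.85·0.15/4000) = 0.6 points. The variance of the risk difference fell by roughly 1% to 8% across the three prognostic rows. A further simulation that also adjusted for diagnosis gave about 85% unadjusted against 85%, 85%, 86% and 88% adjusted, with type I error of 4.8% to 5.5%. Allowing for simulation error, a fair summary is about 0 to 4 points.

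**4. More optimistic assumptions.**

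- A single pre-randomisation score with an assumed AUC of 0.64, 0.70 or 0.76 gave adjusted power of 86%, 88% and 90%, against about 85% unadjusted.
- Using effective N = 270/(1 − R²), R² = 0.10 gives 300 (87.9%) and R² = 0.20 gives 338 (91.3%).

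**5. Chance imbalance.** For a 50% binary factor, the SD of the between-arm difference is √(2·0.5·0.5/135) = 6.1 points. The 95% range is ±1.96·6.1 = ±11.9 points, and the chance of more than 10 points is 10%. If the factor shifts risk by 20 points (assumed), an 11.9-point imbalance moves the crude difference by 0.119·20 = 2.4 points. At an assumed 30 points it is 3.6. The target is 15 points.

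**6. Size of the test at the interim.** Halfway there are about 135 patients and, at the planned rates, 67.5·0.30 + 67.5·0.15 ≈ 30 events. In 20,000 null trials of 136 patients with three covariates, the logistic likelihood-ratio test at nominal 0.005 rejected in 0.59% to 0.64%, against 0.43% to 0.44% for the Pearson test. The excess is small, but it means the choice of test must be stated.

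**The case against.** The strongest reply is that nothing here is broken. Randomisation makes the unadjusted comparison valid, and its error rate already allows for chance imbalance. In a fixed design the trial reaches its stated power without adjustment. The gain depends on prognostic strengths that the documents do not supply, for an endpoint that counts complications of any grade across many organ systems; uninformative covariates would gain nothing. All of this stands, and it limits the point to an improvement.

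Three stronger readings are tempting and are not supported:

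- A reader might infer that the plan has chosen a crude comparison of proportions. It has not said so. The sample size is framed on proportions, but no primary test is named, so adjustment is unspecified rather than rejected.
- A reader might infer that adjustment is free because the data are already collected. The listed blood loss is an operative total that includes loss after randomisation, and extent of resection is not on the visible list. The text around Table 2 is broken in the available copy, so whether extent is recorded elsewhere cannot be settled.
- A reader might expect power of 90%. That needs an AUC of 0.76 for any-grade morbidity, which nothing in the documents supports.

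What remains is that section 14 omits the stratification factor from the primary analysis and leaves that analysis unwritten. That part needs no assumption about prognostic strength.

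**Conclusion.** The point holds as a low-cost improvement. Section 14 names neither a test nor a covariate for the primary comparison and does not say that the diagnosis stratum enters it. Extent of resection and blood loss up to randomisation are valid baseline covariates in this design and are not used.

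The loss is of precision and of robustness to chance imbalance; type I error control does not depend on the adjustment. In a fixed design, adjustment would add about 0 to 4 points of power, assuming odds ratios no larger than 3 for extent and 1.8 per SD for blood loss. An imbalance at the 95% limit in one strong binary factor would move the crude difference by about 2 to 4 points, again under assumed effects of 20 to 30 points.

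**What to change.** Keep the 270 patients and the diagnosis stratification. In section 14:

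- **Model.** Pre-specify logistic regression of 30-day morbidity on arm, diagnosis stratum, extent of resection, and blood loss recorded before the envelope is opened.
- **Estimate.** Report a standardised risk difference with 95% CI, which targets the same marginal quantity as the crude difference, and give the unadjusted comparison alongside.
- **Test.** State which test supplies the p-value at the interim and final looks. With only about 135 patients at the interim, use one whose size holds at 0.005, for example a Mantel-Haenszel test stratified by diagnosis, or verify the size of the chosen test by simulation.

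The cost is analysis-plan wording and two data fields: extent of resection, and blood loss at the moment of randomisation, a figure staff already need for the first replacement volume. If the fields are not added, adjust for the diagnosis stratum alone. Total operative blood loss should not be used as a covariate, because part of it arises after allocation and treatment could affect it.

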16.0 DATA MANAGEMENT ISSUES

All collected data that will only be used for the purposes of the study. It will be maintained in a confidential clinical research database by research study personnel only and under direct

MEMORIAL SLOAN-KETTERING CANCER CENTER IRB PROTOCOL

IRB#: 12-056 A(4)

supervision of the principal investigator. The database will be kept in a password protected computer and will not be transferred outside of the hospital network. A minimum dataset will be kept in CRDB . The data will be linked to the patients by means of unique tracking subject numbers the key to which will be also password protected and only to be accessed by research personnel. Data will be reported to the IRB as required.

16.1 Quality Assurance

Weekly registration reports will be generated to monitor patient accruals and completeness of registration data. Routine data quality reports will be generated to assess missing data and inconsistencies. Accrual rates and extent and accuracy of evaluations and follow-up will be monitored periodically throughout the study period and potential problems will be brought to the attention of the study team for discussion and action. Random-sample data quality and protocol compliance audits will be conducted by the study team at pre-established intervals.

The principal investigator will maintain final responsibility for data during the study and during the final analysis of data. Breaches of protocol, problems with informed consent, or discrepancies in data accuracy will be reported to the IRB as required.

16.2 Data and Safety Monitoring

The Data and Safety Monitoring (DSM) Plans at Memorial Sloan-Kettering Cancer Center were approved by the National Cancer Institute in September 2001. The plans address the new policies set forth by the NCI in the document entitled “Policy of the National Cancer Institute for Data and Safety Monitoring of Clinical Trials” which can be found at:

<http://www.cancer.gov/clinicaltrials/conducting/dsm-guidelines>. The DSM Plans at MSKCC were established and are monitored by the Office of Clinical Research. The MSKCC Data and Safety Monitoring Plans can be found on the MSKCC Intranet at:
<http://mskweb5.mskcc.org/intranet/assets/tables/content/359709/DSMPlans07.pdf>

There are several different mechanisms by which clinical trials are monitored for data, safety and quality. There are institutional processes in place for quality assurance (e.g., protocol

MEMORIAL SLOAN-KETTERING CANCER CENTER IRB PROTOCOL

IRB#: 12-056 A(4)

monitoring, compliance and data verification audits, therapeutic response, and staff education on clinical research QA) and departmental procedures for quality control, plus there are two institutional committees that are responsible for monitoring the activities of our clinical trials programs. The committees: *Data and Safety Monitoring Committee (DSMC)* for Phase I and II clinical trials, and the *Data and Safety Monitoring Board (DSMB)* for Phase III clinical trials, report to the Center's Research Council and Institutional Review Board. During the protocol development and review process, each protocol will be assessed for its level of risk and degree of monitoring required. Every type of protocol (e.g., NIH sponsored, in-house sponsored, industrial sponsored, NCI cooperative group, etc.) will be addressed and the monitoring procedures will be established at the time of protocol activation.

17.0 PROTECTION OF HUMAN SUBJECTS

The responsible investigator will ensure that this study is conducted in agreement with the Declaration of Helsinki (Tokyo, Venice, Hong Kong, Somerset West and Edinburgh amendments). The study will seek in every way to protect the rights of human subjects. The potential risks including adverse drug reactions and potential benefits in terms of reducing transfusion requirement and postoperative recovery will be discussed in detail with patients. Potential side effects as outlined above will be discussed with the patients. No patient will be required to participate in the study and participation or lack of participation will not affect the patient's subsequent care or treatment. The patient will not incur any financial cost as a result of participation in the study. Participation will be purely voluntary and subjects will not be reimbursed for participation in the study. Throughout the study, patient confidentiality will be maintained. No results of the study will be presented or discussed in a fashion that will allow identification of a particular patient in the study. All adverse events will be fully disclosed to the IRB in a timely fashion as required.

17.1 Privacy

MSKCC's Privacy Office may allow the use and disclosure of protected health information pursuant to a completed and signed Research Authorization form. The use and disclosure of protected health information will be limited to the individuals described in the Research Authorization form. A Research Authorization form must be completed by the Principal Investigator and approved by the IRB and Privacy Board.

17.2 Serious Adverse Event (SAE) Reporting

Any SAE must be reported to the IRB/PB as soon as possible but no later than 5 calendar days. The IRB/PB requires a Clinical Research Database (CRDB) SAE report be submitted electronically to the SAE Office at [contact]. The report should contain the following information:

Fields populated from CRDB:

- Subject's name (generate the report with only initials if it will be sent outside of MSKCC)
- Medical record number
- Disease/histology (if applicable)
- Protocol number and title

Data needing to be entered:

- The date the adverse event occurred
- The adverse event
- Relationship of the adverse event to the treatment (drug, device, or intervention)
- If the AE was expected
- The severity of the AE
- The intervention
- Detailed text that includes the following
 - A explanation of how the AE was handled
 - A description of the subject's condition
 - Indication if the subject remains on the study
 - If an amendment will need to be made to the protocol and/or consent form.

The PI's signature and the date it was signed are required on the completed report.

17.2.1 NA

18.0 INFORMED CONSENT PROCEDURES

Before protocol-specified procedures are carried out, consenting professionals will explain full details of the protocol and study procedures as well as the risks involved to participants prior to their inclusion in the study. Participants will also be informed that they are free to withdraw from the study at any time. All participants must sign an IRB/PB-approved consent form indicating their consent to participate. This consent form meets the requirements of the Code of Federal Regulations and the Institutional Review Board/Privacy Board of this Center. The consent form will include the following:

1. The nature and objectives, potential risks and benefits of the intended study.
2. The length of study and the likely follow-up required.
3. Alternatives to the proposed study. (This will include available standard and investigational therapies. In addition, patients will be offered an option of supportive care for therapeutic studies.)

MEMORIAL SLOAN-KETTERING CANCER CENTER
IRB PROTOCOL

IRB#: 12-056 A(4)

4. The name of the investigator(s) responsible for the protocol.
5. The right of the participant to accept or refuse study interventions/interactions and to withdraw from participation at any time.

Before any protocol-specific procedures can be carried out, the consenting professional will fully explain the aspects of patient privacy concerning research specific information. In addition to signing the IRB Informed Consent, all patients must agree to the Research Authorization component of the informed consent form.

Each participant and consenting professional will sign the consent form. The participant must receive a copy of the signed informed consent form.

